1.2. Research Hypotheses

1. Novel wearable sensors (i.e, Bittium Faros, Biovation Everion, and Profusa Lumee) can detect physiologic changes that are associated with influenza infection and disease severity.
2. Physiologic patterns of heart rate, physical activity, ECG, respiratory rate and oxygen saturation from wearable sensors can act as biomarkers that enhance current diagnostic practice for early detection of influenza infection and disease prediction.

STUDY OBJECTIVES

1.3. Primary Objective:

- To test the hypothesis that measurements of heart rate, physical activity, ECG, respiratory rate and oxygen saturation can detect influenza infection and disease

1.4. Secondary Objective:

- To identify early signatures using sensor data that predict influenza disease and severity, potentially enabling earlier medical or public health interventions

1.5. Exploratory Objectives:

- To test the associations between physiologic sensor measurements and cognitive function using objective tests
- To test the associations between physiologic sensor measurements and biological and immune readouts

PARTICIPANT ENTRY

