1.17.2. Bittium Faros sensor

The Bittium (formerly eMotion) 180° Faros sensor monitors heart rate variability, electrocardiography and physical activity. The sensor box (Figure 1) will be attached to the chest with two disposable, adhesive electrodes positioned on the chest. The device is CE-marked (93/42/EEC) and is in accordance with MDD Class IIa. The sensor and electrodes are not waterproof and will need to be removed before showers etc. They are also not suitable to use in an MRI environment. The device is not intended to be used along high frequency surgical equipment or a defibrillator. The device will require charging via docking station and data will be downloaded intermittently via USB cable to a computer by study personnel at study visits. After successful connection of the sensor, study personnel will explain and train subjects on how to use the Faros as well as ensuring study subjects understand usage, handling and maintaining of the device and electrodes. An initial data collection process will be undertaken to check that the Faros is working correctly prior to the end of the study visit.

Figure 1: Bittium Faros sensor and positioning.

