1.17.3. Biovotion Everion sensor

The Biovotion Everion (Figure 2) is a CE marked, non-invasive wearable multi-sensor device that monitors heart rate, skin temperature, respiration rate, steps, activity, and energy expenditure from the skin's surface. It will be attached to the left or right upper arm using an armband and will be in contact with intact skin only. All measurements are taken on the surface of the skin. Data from the device is collected via the Biovotion application, which will be pre-loaded to the mobile device provided. Each participant will have a study user account created with identification only by subject study ID. After successful connection of the sensor and mobile device, study personnel will explain and train subjects on how to use the Biovotion Everion and the features of the Biovotion application as well as ensuring study subjects understand usage, handling and maintaining of the Biovotion Everion. An initial data collection process will be undertaken to check that the Biovotion Everion is working correctly prior to the end of the study visit. The following parameters will be collected: activity, barometric pressure barometer temperature, skin blood perfusion index, blood pulse wave, energy expenditure, galvanic skin response, heart rate, heart rate variability, local temperature, skin temperature, respiration rate, blood oxygenation and steps per day.

Figure 2: Biovotion Everion device, charger/docking station and armband positioning.

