We aim to determine if the different sensors in the study can measure changes associated with influenza infection. For each sensor we will define and compute multiple metrics from the raw sensor output. Each of these metrics will be compared in the healthy versus sick states for each subject. We will consider a metric to be a potential predictor of illness in a single subject if there is a significant ($p < 0.05$) difference between the mean value in the sick and healthy state. Control comparisons will be made by computing the significance of differences between two different healthy periods (e.g. prior to infection and post recovery).

The potential predictors of illness from the within subject analysis will be compared across all subjects to determine if any sensor metrics provide generalizable indicators of illness. A metric will be considered a valid indicator if it is present in at least 85% of the within subject sick/healthy comparisons and less than 25% of the within subject control comparisons. This odds ratio is sufficient to achieve 80% power and a 5% error rate with a sample size of 13 subjects. Based on an established attack rate of 75% with this challenge virus, we estimate that will have 15 of our 20 subjects develop influenza. Therefore, the sample size of this study is sufficient to determine the feasibility of using the selected sensors to measure changes associated with influenza.

Data and all appropriate documentation will be stored for a minimum of 10 years after the completion of the study, including the follow-up period according to Imperial College London policy.

REGULATORY ISSUES

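### The sensor metrics are not fixed in advance and are declared valid on the participants used to select them, so metrics short of the 85% bar can pass and the winner's detection rate is overstated; the quoted 5%/80% does not describe the rule

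*Combined protocol and SAP*

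**What the plan says.** Section 1.3 makes the primary objective a hypothesis test on five kinds of measurement: "To test the hypothesis that measurements of heart rate, physical activity, ECG, respiratory rate and oxygen saturation can detect influenza infection and disease". The Statistics and Data Analysis section carries it out in two steps.

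- **Within each participant:** "For each sensor we will define and compute multiple metrics from the raw sensor output". Each metric's mean is compared between the sick and healthy states at p < 0.05. Control comparisons set two healthy periods against each other.
- **Across participants:** the results are pooled "to determine if any sensor metrics provide generalizable indicators of illness". A metric is a valid indicator if it is flagged in at least 85% of sick/healthy comparisons and in fewer than 25% of control comparisons.

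The error statement attached to the rule is: "This odds ratio is sufficient to achieve 80% power and a 5% error rate with a sample size of 13 subjects". The section expects 15 of 20 participants to develop influenza.

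The documents give no list or number of metrics, no formulas, no primary metric or order, no direction of change and no validation set. Section 1.17 shows how wide the choice is. Faros "monitors heart rate variability, electrocardiography and physical activity". For Everion: "The following parameters will be collected: activity, barometric pressure barometer temperature, skin blood perfusion index, blood pulse wave, energy expenditure", and then "galvanic skin response, heart rate, heart rate variability, local temperature, skin temperature, respiration rate, blood oxygenation and steps per day". Lumee reads tissue oxygen at two body sites.

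**The concern.** An analyst may define as many metrics as seem useful, look at all of them in the same few ill participants, and report those that clear the bar. Nothing prevents a definition from being tuned on the participants who then validate it. Activity and heart rate variability each come from two devices and oxygen from two Lumee sites, so one objective has several routes to success and no rule for when they disagree.

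The plan's only error statement makes no allowance for this. A reader will take 5% and 80% as properties of the declaration rule, and they are not. At stake is the observed detection rate of the winning metric. It would be reported as meeting the plan's own 85% standard and passed on to algorithm development (section 1.1), although selection among many metrics pushes it upward.

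**Working it through.** **Inputs from the documents.** Cut-offs 85% and 25%; 5% error, 80% power, 13 participants; 15 ill participants expected (Statistics and Data Analysis).

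**Assumptions.** The number of metrics is not given. I use 17, a count of named channels: Faros 3, Everion 12 (14 listed items less the two barometer items), Lumee 2 sites. True rates and correlations between metrics are also assumed. Sick and control comparisons are treated as independent.

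**1. Reproducing the 13.** Two-sided comparison of two proportions, mean proportion 0.55:

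n = [1.96·√(2·0.55·0.45) + 0.84·√(0.85·0.15 + 0.25·0.75)]² / 0.60² = (1.379 + 0.472)² / 0.36 = 9.52

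With continuity correction: (9.52/4)·[1 + √(1 + 4/(9.52·0.60))]² = 12.63, rounded up to 13. The stated figure is reproduced exactly, as one test on one metric.

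**2. What the written rule does.** A metric passes with probability P(X ≥ a)·P(Y ≤ b), with X and Y binomial. For n = 13, a = 12 and b = 3; for n = 14, a = 12 and b = 3; for n = 15, a = 13 and b = 3.

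- *True rates exactly 85% and 25%:* 0.398 × 0.584 = 0.23 at n = 13, and 0.604 × 0.461 = 0.28 at n = 15. The 80% is not the rule's power.
- *Same true rate in sick and control comparisons (no signal):* the largest pass probability over all common rates is 0.00010 (n = 13), 0.00020 (n = 14) and 0.00007 (n = 15). Over 17 independent metrics the worst case is 1 − (1 − 0.00020)^17 = 0.33%; over 100 it is about 2.0%. The 5% is not the rule's error rate either.

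**3. Metrics with real but insufficient signal.** Take 70% in sick and 10% in control comparisons, n = 15:

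- One metric: P(X ≥ 13) = 0.127, P(Y ≤ 3) = 0.944, product 0.120.
- At least one of 17, independent: 1 − (1 − 0.120)^17 = 0.89.
- Correlated metrics, by simulation with equally correlated normal variables:

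| Correlation | At least one of 17 passes | Mean observed sick rate of the best of 17 (true 70%) |
|---|---|---|
| 0 | 89% | 90% |
| 0.5 | 67% | 86% |
| 0.8 | 49% | 83% |

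*Sensitivity.* With three independent metrics, one per sensor: 1 − (1 − 0.120)³ = 32%. With true rates of 60% and 10%: 2.6% for one metric, and 36%, 25% and 17% for 17 metrics at correlations 0, 0.5 and 0.8. With n = 13 and 70%/10%: 0.0637 × 0.966 = 0.061 for one metric, and 66% for 17 independent metrics.

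**4. Does the remedy work?** In the same 70%/10% simulation, choosing the metric with the highest sick rate among the other 14 participants and scoring it on the one left out returns about 70% at all three correlations. The optimism is removed.

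**The case against.** Three points favour the plan.

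First, a reader might infer that each metric has a 5% chance of false declaration, so that 17 metrics give 1 − 0.95^17 = 58%. The documents do not support this. A metric is declared by the two-part count rule, not by a test at 5%, and step 2 shows how rarely noise meets that rule. This point stands in full, with one caveat: the bound assumes equal true rates in sick and control comparisons. Confinement or daily sampling could shift a metric in the sick window only. That is confounding, a separate matter, though more metrics give it more chances.

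Second, a metric with rates of 70% and 10% does detect illness. Its odds ratio is (0.70/0.30)/(0.10/0.90) = 21, against (0.85/0.15)/(0.25/0.75) = 17 for the plan's cut-offs. Passing it is not a false positive against the primary objective. This also stands. What remains is that it misses the plan's own 85% standard and would be reported as meeting it.

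Third, the same section calls the study proof of concept, says a formal power analysis is not possible and leaves generalizable detection statistics to larger studies. That lowers the severity. It does not settle the matter: the next paragraphs still look for generalizable indicators, use the label *valid* and attach a 5% error rate, and the exploratory objectives in section 1.5 cover only cognitive and immune associations.

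The count of 17 is also open to challenge, since some Everion channels are not clearly among the five measurement types in the objective. With three metrics the chance of a pass is still 32%, against 12% for one (independent metrics).

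**Conclusion.** The point holds as one of pre-specification and selection optimism, and is a should-fix. The metric set is open, no metric leads, and selection and validation use the same participants. The 5%/80% statement belongs to a single two-proportion comparison.

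Under the assumed 70%/10% rates, 15 ill participants and 17 metrics, at least one metric passes with probability 49% to 89%, and the best observed rate averages 83% to 90%, for correlations from 0.8 down to 0. These sizes depend on the assumed rates, number of metrics and correlations, none of which the documents give. The direction of the bias does not depend on the exact values. The reproduction of 13 and the rule's pass probabilities at 85%/25% use only the plan's figures, apart from two-sidedness and independence of sick and control comparisons.

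The documents do not support a claim that the chance of declaring a pure-noise metric is far above 5%.

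**What to change.** 1. Before any post-inoculation sensor data are analysed, date and fix the metric list: formula, device, body site, direction of change, and the sick and healthy windows. Mark one lead metric per sensor where one can be justified. If the earlier pilot data are used for that choice, note that they came from different, non-commercial devices (section 1.1).
2. Reserve the term *valid indicator* for the pre-listed lead metrics. Call all others *candidate indicators*, in line with the proof-of-concept aim.
3. For any metric selected or tuned on these data, report leave-one-participant-out detection and control rates, with the selection step repeated inside each fold. Add a permutation p-value from the maximum statistic over the full metric list, exchanging sick/healthy and control comparisons within participants.
4. State that the 5% error rate and 80% power are for a single comparison of 85% with 25%, and not for the rule or for selection among metrics.

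The cost is analysis-plan wording, a short dated list and computing time, with no extra participants or procedures. The downside is weaker labels for most metrics and less favourable reported rates.

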This study will follow on from our previous Prometheus study, which systematically investigated the early pre-symptomatic period following exposure to influenza in humans and provided exploratory pilot data with non-commercial sensor devices that suggested that sleep disturbance occurred within 24 hours of influenza exposure. The data obtained in this study will be used to test the ability of novel wearable sensors to detect changes associated with infection and disease severity, thus allowing their use in general settings to predict which individuals will go on to more severe symptoms and higher viral shedding, enabling implementation of treatments and other interventions at an earlier stage. Ultimately these data will inform the development of a fully automated, network of human-based wearable sensors that detect biomarkers indicative of respiratory infection and level of severity, and transmit acquired signals to corresponding smartwatches or phones. Current public health networks track only patients who seek medical care. The total time associated with the development of infection symptoms, laboratory-based diagnostic tests, data compilation, and reporting results in a 3–5 week delay in the detection of the disease outbreak. By using human-based, wearable, networked sensors in concert with point-of-care diagnostics and automated data collection and reporting, the time required to detect disease outbreaks may be shortened by weeks. A required innovation is the development of algorithms for illness detection and severity estimation that distinguish host response from confounding factors such as increased mental or physical demands. This study will provide essential data for the development of these algorithms with the acquisition of sensor data from the pre-symptomatic phase of influenza through recovery. The collection of HRV data from multiple sensors will allow for comparison of ECG sensors to wrist and arm sensors that may be more convenient for long-term wear. The integration of physical activity measures will enable evaluation on subjects without activity restrictions.

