1.11. Study visits

The study is divided into outpatient and confinement phases. Subjects will stay overnight for a period of 8-11 nights in total, from the morning before the viral challenge, to the 8-10th day after viral challenge. This period of confinement has been chosen to eliminate the possibility of subjects in the study transmitting the virus to anyone not involved in the study (i.e. family, household contacts, and the wider community). Confinement is not used to enable closer monitoring or to enhance safety for study subjects, although this may be an additional benefit in some circumstances. During the confinement period, all study procedures will take place in the confinement facility (Table 1). There will also be follow-up visits (1.11.3).

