1.11.1. Pre-inoculation visits (ICRRU/ICRF, day -7 and day -3)

On the day -7 (pre-inoculation) visit nursing or medical staff will perform lung function, blood tests, a throat swab, take washings from the participant's nose (nasal lavage), a nasal scrape, nasal brushing, and a nasal SAM. The Lumee device will be inserted and the Faros, and Biovotion sensors will also be given to the volunteer. At day -7 the participant will also be given a symptom diary card and asked to complete it (before any nasal procedures), detailing any respiratory symptoms they experience in their upper and lower airways. They will be asked to complete the symptom diary on a daily basis for one week prior to and two weeks after inoculation with the virus.

On the day -3 (pre-inoculation), we will perform lung function, blood tests, a throat swab, take washings from the participant's nose (nasal lavage), a nasal scrape, nasal brushing, and a nasal SAM. The wearable sensors will be checked for functionality and data will be downloaded if necessary.

Subject to a satisfactory assessment by the study doctor (brief interview and medical examination) and the taking of blood and nasal lavage samples, we will infect volunteers with influenza on day 0. Those challenged with influenza will then be confined as described (Section 1.10.2).

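### The sensor rule does not separate influenza from confinement: healthy data come mostly from home and sick data from the unit, the control windows are not fixed by setting, and the uninfected have no stated role

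*Combined protocol and SAP*

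**What the plan says.** The sensor analysis is in Statistics and Data Analysis. For every metric, "Each of these metrics will be compared in the healthy versus sick states for each subject". A metric counts for a subject if there is a significant (p < 0.05) "difference between the mean value in the sick and healthy state". The safeguard is a second within-subject test: "Control comparisons will be made by computing the significance of differences between two different healthy periods (e.g. prior to infection and post recovery"). A metric is a valid indicator if it appears in "at least 85% of the within subject sick/healthy comparisons and less than 25% of the within subject control comparisons". The plan calls this contrast "sufficient to achieve 80% power and a 5% error rate with a sample size of 13 subjects" and expects 15 of 20 participants to develop influenza.

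On setting, section 1.11 states: "The study is divided into outpatient and confinement phases". Confinement runs from the morning before challenge to day 8-10. At the day -7 outpatient visit (section 1.11.1), "The Lumee device will be inserted and the Faros, and Biovotion sensors will also be given to the volunteer". Section 1.11.2 makes discharge on the 8th day of residence depend on significant symptoms having resolved, and says that only the symptom diary continues at home. As far as it can be read, Table 1 marks Faros and Everion to day 10 and the Lumee reader to day 14.

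The background (section 1.1) says that detection algorithms must tell host response apart from confounders such as physical demand. It adds: "The integration of physical activity measures will enable evaluation on subjects without activity restrictions". Neither point is carried into the decision rule.

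**The concern.** Within a subject, going from healthy to sick also means going from home to unit. Everion records steps, activity, energy expenditure, heart rate and heart rate variability, and Faros records the ECG and activity. These can plausibly change when someone moves into a residential unit, with or without influenza. The rule neither matches nor adjusts for setting.

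The control comparison could protect against this only if it contained the same change of setting, and the plan does not say whether it does. If both healthy windows are at home, it cannot see a confinement effect. If the second is in the unit, it reacts to setting and counts that against the metric, even when the metric also detects influenza.

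The primary objective is whether these measurements detect influenza. As the rule stands, a metric could pass because of confinement or fail because of it. Where the control window falls decides which, and that choice is left open.

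**Working it through.** **The plan's own figure.** For 85% versus 25%, two-sided 5% and 80% power, the odds ratio is (0.85/0.15)/(0.25/0.75) = 17. The log-odds-ratio formula gives n = (1.960 + 0.842)² × [1/(0.85×0.15) + 1/(0.25×0.75)] / (ln 17)² = 7.85 × 13.18 / 8.03 = 12.9, so 13. The continuity-corrected two-proportion formula also gives 13. The arithmetic is sound. It does, however, use the control rate as the rate without illness, and that is right only if the control carries the same change of setting as the sick/healthy comparison.

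**Inputs from the documents.** Days -7 to -2 are at home (6 days) and day -1 is in the unit. With 13 subjects the rule needs at least 12 sick/healthy flags (0.85×13 = 11.05) and at most 3 control flags (0.25×13 = 3.25). With 15 it needs at least 13 (12.75) and at most 3 (3.75).

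**Assumptions, not in the documents.** One summary value per day; a two-sided t-test in each subject; 5 sick days in the unit; an admission shift of d within-person day-level SD, the same in everyone; independent subjects; a 5% flag rate where nothing changes.

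**Per-subject flag probability.** This is P(|T| > critical value), with T noncentral t, n1+n2-2 degrees of freedom and noncentrality d × √(n1·n2/(n1+n2)).
- 6 home vs 5 unit days: noncentrality 1.651d, critical value 2.262.
- 6 home vs 3 unit days (assumed post-recovery window): noncentrality 1.414d, critical value 2.365.

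**Case A: both control windows at home, no influenza effect.** P(valid) = P(enough sick/healthy flags) × P(at most 3 control flags at 5%). The second factor is 0.997 for 13 subjects and 0.994 for 15.

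| d | flag rate, 6 vs 5 | P(valid), n=13 | P(valid), n=15 |
|---|---|---|---|
| 1 | 0.315 | <0.0001 | <0.0001 |
| 1.5 | 0.598 | 0.01 | 0.03 |
| 2 | 0.836 | 0.34 | 0.54 |
| 2.5 | 0.955 | 0.88 | 0.97 |
| 3 | 0.992 | 0.99 | 0.99 |

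**Case B: post-recovery control window in the unit.** The control now flags for setting.

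| d | control flag rate, 6 vs 3 | P(more than 3 of 15 flagged) |
|---|---|---|
| 1 | 0.232 | 0.47 |
| 1.5 | 0.449 | 0.96 |
| 2 | 0.681 | >0.99 |

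A genuine influenza metric that also responds to confinement is rejected with the probability in the last column. A confinement-only metric is blocked: at d = 2 and n = 13 its P(valid) is about 0.0004.

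**Which case applies.** With discharge on day 8, 9 or 10, Faros and Everion have 10-8 = 2, 1 or 0 home days left in Table 1. The Lumee reader has 14-8 = 6, 5 or 4. If only the diary continues at home, no device has any.

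**The uninfected.** The expected number is 20 × 0.25 = 5, and P(2 or fewer) = 0.09 from Bin(20, 0.25). For 15 vs 5, one change value per person, noncentrality is 1.5 × √(75/20) = 2.90 on 18 degrees of freedom, giving 78% power at 1.5 between-person SD of change. The 95% interval half-width is 2.101 × √(1/15 + 1/5) = 1.08 SD.

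**The case against.** A reader might infer that the plan is likely to certify confinement artefacts as influenza indicators. The documents do not support that. It needs home-versus-home control windows and a shift of about 2 SD or more, and no section reports an admission effect of any size. The devices most exposed to a change of setting, Faros and Everion, have at most two home days after discharge in Table 1. Their before-and-after control would then be largely home versus unit, which blocks a confinement-only metric. For them the likelier error is rejecting a genuine metric.

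A reader might also infer that the uninfected are excluded. They are not: the text speaks of each subject and of all subjects. But they have no sick state and no rule covers them.

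The study is a proof of concept that defers generalizable detection statistics to larger studies. That excuses imprecision. It does not make the rule's answer interpretable.

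The uninfected are also an imperfect control. The plan applies the 75% attack rate to symptomatic infection in one paragraph and to developing influenza in the next, so the remaining 5 may include asymptomatic infections. This argues against using them as a hard pass/fail test, but not against using them.

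**Conclusion.** The concern holds as a failure to separate infection from confinement, with the direction of error left open. With home-versus-home controls, the chance of a false valid indicator runs from near 0 at 1 SD to 0.99 at 3 SD. With the post-recovery window in the unit, the chance of rejecting a genuine metric that also responds to setting is 0.47 at 1 SD, 0.96 at 1.5 SD and above 0.99 at 2 SD. All of these figures rest on the assumed shift, daily summaries, window lengths and a common shift across subjects. What does not rest on them is the design fact: about 6 of 7 pre-inoculation days are at home, nearly all sick days are in the unit, and no planned analysis compares infected with uninfected participants living the same confinement days. It should be settled before sensor data are analysed.

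**What to change.** 1. Before sensor data are analysed, define the healthy, sick and control windows by study day and by setting, for each device.
2. Run the same day-window comparison in challenged participants who are PCR-negative throughout, classified by virology and not by symptoms. For each metric, report the infected-minus-uninfected difference in within-person change, one value per participant, with a permutation or exact test and an interval.
3. Do not describe a metric as a valid influenza indicator where the uninfected show a similar change. Judge this from the estimate and its interval, as supporting evidence, and not from a fixed count of flags in about 5 people.
4. Use the in-unit pre-inoculation period only as a descriptive sensitivity check, because it lasts about one day and is the admission day itself.
5. Reconcile the text on timing. Section 1.11 and the introduction to Study Procedures place participants in the unit from day -1, while section 1.11.2 describes entry after inoculation. Section 1.11 counts days after challenge, while 1.11.2 counts days of residence. Table 1 and section 1.11.2 differ on sensor wear after discharge.

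The cost is analysis-plan wording, a stated virological definition of infection (the statistics section has none) and modest extra analysis, with no new visits or participants. The downside is precision: about 5 uninfected are expected, with a 9% chance of 2 or fewer, and fewer still if the 75% refers to symptomatic infection only.

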If a participant loses capacity during the study, then the participant would be withdrawn from the study. Identifiable data or tissue already collected with consent would be retained and used in the study. No further data or tissue would be collected or any other research procedures carried out on or in relation to the participant.

The study is a low-risk non-CTIMP, carried out by an experienced PI and study team. The study has appropriate risk assessments in place and will be checked through the PRB system at ICRF.

Local monitoring will be carried out by study staff to ensure that CRFs are being completed, with no key data missing. Duke University will appoint one of their in house monitors to check the data produced, paper CRFs will be uploaded to their eCRF system. The monitor will check consent forms and data logs.

STATISTICS AND DATA ANALYSIS

Sample size estimation: the goal of this study is a proof-of-concept demonstration that physiological measures can detect influenza infection in the pre-symptomatic phase. As such, it is not possible to carry out a formal power analysis to determine the sample size, since no preliminary data on the effect size in influenza infection using the sensors in this study are available. However, heart rate variability (HRV) parameters have been shown to enable detection of sepsis with 86% sensitivity and 100% specificity in a study of 17 subjects (14 positive and 3 negative for sepsis)⁵. Therefore, we aim for a similar target for numbers of symptomatically infected individuals (13-15), which is likely to be achieved with a sample size of 20 subjects based on the previously established attack rate of 75% using this challenge virus. Larger studies would be required in the future to generate generalizable detection statistics, but the 20-subject sample size proposed here should be sufficient for concept demonstration.

Quantitative assessments of symptom scores, lung function, virus load, leukocyte numbers and inflammatory markers will be compared within subjects to determine differences between baseline and during infection. Intra-subject differences will be analysed using ANOVA and 2-tailed paired Student's t-tests or Wilcoxon signed rank test as appropriate. Correlations between inflammatory cell, illness severity, viral load and leukocyte counts will be examined using Spearman's rank correlations to investigate possible causal relationships.

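### Across participants the sensor metrics are judged only by counting per-person p<0.05 flags, so the plan yields no estimate of how much any metric changes and can lose substantial power; a paired analysis should be added alongside the count.

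*Combined protocol and SAP*

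**What the plan says.** All the relevant text is in the Statistics and Data Analysis section of the combined protocol and SAP. The sensor analysis has three steps.

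- **Within a person.** Several metrics are computed per sensor. The flag is defined thus: "We will consider a metric to be a potential predictor of illness in a single subject if there is a significant" result, at p<0.05, when that person's sick and healthy means are compared. Sidedness is not stated, and nothing requires the direction to agree between people.
- **Control.** "Control comparisons will be made by computing the significance of differences between two different healthy periods", for example before infection and after recovery.
- **Across people.** To be accepted as an indicator, a metric's flag must be "present in at least 85% of the within subject sick/healthy comparisons and less than 25% of the within subject control comparisons".

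The plan adds: "This odds ratio is sufficient to achieve 80% power and a 5% error rate with a sample size of 13 subjects". On numbers: "we estimate that will have 15 of our 20 subjects develop influenza".

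The same section treats symptom scores, lung function, viral load, leukocytes and inflammatory markers differently: "Intra-subject differences will be analysed using ANOVA and 2-tailed paired" t-tests, or the Wilcoxon signed rank test. Sensor metrics are not in that list. The section also says that no preliminary effect-size data exist for these sensors in influenza.

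**The concern.** Heart rate, heart rate variability, respiratory rate, activity and oxygen are continuous and recorded repeatedly in each person. Cutting each person's change at p<0.05 treats a change just short of the line as nothing and a very large change as no more than a borderline one. A rise and a fall count alike. The across-person inference then rests on a count out of 13 to 15.

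The primary objective (section 1.3) depends on these metrics, yet they get a coarser cross-participant analysis than the clinical and laboratory measures. Two things are at stake:

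- Metrics with a real and consistent change may be missed in a small sample. Section 1.10 rules out replacing participants after Day 0.
- The trial would report no mean change with a confidence interval for any metric. The plan defers generalisable detection statistics to larger studies, and those studies would need such estimates for their sizing. This second loss depends on no power assumption.

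**Working it through.** **1. The plan's own figure.** Inputs from the plan: p1 = 0.85, p2 = 0.25, 5% error, 80% power. For two independent proportions, two-sided:

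n = [1.960·√(2·0.55·0.45) + 0.842·√(0.85·0.15 + 0.25·0.75)]² / 0.60² = (1.379 + 0.472)² / 0.36 ≈ 9.5, which rounds up to 10.

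With continuity correction: n = (9.52/4)·[1 + √(1 + 4/(9.52·0.60))]² ≈ 12.6, which rounds up to **13**. The stated 13 reproduces. This formula treats the sick and control flags as separate groups, although both come from the same people.

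**2. The stated rule at those rates (exact binomial, independent flags).**

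| Infected | Sick flags needed | Control flags allowed | P(sick part) | P(control part) | P(both) |
|---|---|---|---|---|---|
| 13 | ≥12 (11/13 = 84.6% fails) | ≤3 (4/13 = 30.8% fails) | 0.398 | 0.584 | **0.233** |
| 15 | ≥13 (12/15 = 80% fails) | ≤3 (4/15 = 26.7% fails) | 0.604 | 0.461 | **0.279** |

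**3. Flags against the full-scale change.** The documents give no effect size, so a model must be assumed:

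- Each person's standardised change z is normal and is flagged if |z| > 1.96.
- Control z has mean 0 and SD 1.704, which gives P(|z| > 1.96) = 0.25.
- Sick z has a common direction, with the mean solved so that P(|z| > 1.96) = 0.85: mean 3.72 at SD 1.70, 4.55 at 2.56, 5.25 at 3.41 and 5.79 at 4.26.
- Correlation between sick and control z is 0 or 0.3. There were 40,000 simulated trials per setting.

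The full-scale test is a paired t-test on sick change minus control change. The flag test is an exact two-sided McNemar test, chosen here because the plan names no cross-participant test.

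| Infected | Paired t | McNemar on flags | Stated rule |
|---|---|---|---|
| 13 | 98.6-100% | 77-78% | about 23% |
| 15 | 99.5-100% | 85-87% | about 28% |

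With uncorrelated changes McNemar has about 78% and 86-87%. The gap to McNemar is therefore about 20 points at 13 and about 13 at the expected 15.

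**4. Where the gap closes or reverses.**

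- *Opposite directions, n = 15, SD 1.70.* With 10% of participants moving the other way, paired t has 86% and McNemar 86%. With 20%, paired t has 55% and McNemar 86%.
- *Very uneven changes, n = 13, 85% sick flags, between-person SD 8 in units of the within-person standard error.* Paired t has 63-65% and McNemar 78%.
- *Nearly everyone flagged (98% sick, 5% control).* The stated rule passes 97% (n = 13) or 99% (n = 15) of the time, against 100% for paired t. The loss is 1-3 points.

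**The case against.** **The flag count answers a legitimate question of its own.** The plan wants to know in how many individuals illness is detectable. That fits its interest in detection algorithms and its sepsis benchmark of 86% sensitivity and 100% specificity. A mean shift shows something else. This stands, and it means the count should not be replaced or demoted.

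**Failing a moderate metric is not an error.** A reader might take the moderate cases as further power loss. If 60% of participants would be flagged when sick, then at n = 13 paired t has 70-90% power (SD 2.56 and 1.70) against 25% for McNemar. But such a metric falls short of the plan's 85% requirement by design, and rejecting it is the intended result.

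**A reader might infer a guaranteed loss of at least 20 points.** The documents do not support that. They contain no effect size, spread or direction. Even on the model above, the gap at the expected 15 infected is about 13 points, and it can vanish or reverse. Against the plan's stated 80% power, 20 points is the most that any analysis could gain.

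**The 23% and 28% are not all due to the cut at p<0.05.** They arise largely because the thresholds equal the assumed true rates. They are probabilities of meeting a rule, not the power of a test.

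**A mean test per metric brings multiplicity.** The plan computes several metrics per sensor, so attaching a 5% error to each would let false positives accumulate. This stands, and the remedy must deal with it.

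**Sensor data are used elsewhere.** The aims and exploratory objectives relate them to viral, immune and cognitive measures. However, no statistical method is named for the sensor part of those analyses, and none would estimate the change with infection.

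**Conclusion.** The point holds as a gap in the analysis of the primary-objective measures. The size and direction of each person's sensor change are discarded, and no pooled change with a confidence interval is planned, although suitable paired methods are already named for other measures. This follows from the text alone.

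The power consequence can be substantial but has no fixed size. At the plan's own rates it is about 20 points at 13 infected and about 13 at 15, against a McNemar test on the flags. Those figures rest on normal changes, a common direction, the spreads listed and a comparator that the plan does not name.

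The case supports adding an analysis. It does not support dropping the 85%/25% rule or moving the formal error rate away from it.

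**What to change.** In the Statistics and Data Analysis section, alongside the flag rule, add for each sensor metric:

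1. Each participant's mean sick-minus-healthy change and the matching healthy-minus-healthy control change, on the original or log scale.
2. A comparison of the two across participants by the paired t-test or Wilcoxon test already named in that section, or by a mixed model with a participant random effect.
3. The mean difference with its 95% confidence interval.
4. Either a stated multiplicity control across metrics or a statement that these tests are exploratory.

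Keep the 85%/25% count as the measure of individual-level detectability.

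The cost is a few sentences and a little extra analysis of data already being collected, with no added participants, visits or procedures. The drawback is that a signed mean is less sensitive where people change in different directions. The retained count would still show such changes.
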